Therefore, for CRBSI to be diagnosed, patient must have criteria 1 OR 2 plus 3 OR 4.

Finally, CAUTI will be defined if **all** the following are present (Nicolle, Antimicrob Resist Infect Control 2014):

1. One or more organisms are present at quantitative counts $\geq 10^5$ colony-forming units/mL from an appropriately collected urine specimen
2. The attending physician believes there is an acute infection and prescribes antibiotics
3. There is no other plausible source of infection at the time the diagnosis of CAUTI is made

The number of antibiotic free days at 28 days will be defined as 28 less the number of days the patient received antibiotics.

All events will be adjudicated by the coordinating center.

3.4) Sample size

This is a pilot study including 100 unique patients. The density of incidence of sepsis and other device-related infection (VAP, CRBSI and CAUTI) will be calculated as the number of events over the total number of patients/day at risk. For the primary outcome of incidence of sepsis, this sample size will be able to inform 95% credible intervals with approximately 3 events per 100 patient-days overall (4 events per patient-day per group), and interval length based on Bayesian *Poisson* regression model with intercept parameter assuming non-informative normal prior centered in 8 event per 100 patient-days incidence rate, $N(e^{0.08}, 5)$.

The prior has a very large standard deviation, giving virtually no importance to its average choice, which was established assuming a slightly worse scenario than was described for a European population of 5 events per 100 patient-days (Allegranzi, 2011).

4. Analyses set

Study protocol mentioned that analysis will be done considering the intention to treat principle. However, during study conduction, some randomized patients did not require simultaneous insertion of all three devices (ETT, CVC and UC) due to illness severity, or the attending physician decided not to insert the devices. Those cases were excluded from the analyses. Consequently, main analysis will be carried out considering a Per Protocol Set (PPS) above. Our expectations are that per protocol and full compliance sets will be the same. Nevertheless, if it happens otherwise, full compliance set must be used to evaluate efficacy measures (infection incidences) and per protocol set to evaluate security measures (adverse events).

4.1) Per Protocol Set

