All patients that were randomized, fulfill all inclusion and exclusion criteria, and receive the three devices (ETT, CVC and UC) from allocated arm (coated or habitual) at least one time.

4.2) Full compliance set

All patients that were randomized, fulfill all inclusion and exclusion criteria, and receive the three devices (ETT, CVC and UC) from allocated arm (coated or habitual) all the times that were needed.

5. Analyses Methods

Continuous data will be reported as mean (standard deviation) or median (quartiles) as appropriate. Categorical variables will be described by absolute and relative frequencies.

5.1) Baseline characteristics

Patients' baseline characteristics will be presented without any hypothesis test comparing patients allocated to Coated versus Habitual devices.

5.2) Primary outcome

As described at section 3.4 (sample size), the primary outcome of incidence of sepsis, will be estimated via Bayesian *Poisson* regression model with intercept parameter assuming non-informative normal prior centered in 8 event per 100 patient-day incidence rate, $N(e^{0.08}, 5)$.

5.3) Exploratory outcomes

The same Bayesian *Poisson* regression model with intercept parameter assuming non-informative normal prior centered in 8 event per 100 patient-day incidence rate, $N(e^{0.08}, 5)$, will be done to estimate other infection incidences (VAP, CRBSI, CAUTI).

Besides, the same model will be used to compare patients that used coated devices versus habitual devices. Results will be reported as Risk Ratios (RR) with 95% Credible Intervals. Models will be adjusted for admission type, baseline SOFA and the stratification variable (presence of sepsis at randomization).

Results will be reported considering adjudicated events and events reported by the centers. Sepsis, as reported by centers will be considered as: two point increase in SOFA plus newest use of ATB. The end of sepsis will be considered at the time of ATB withdrawal concomitant with any improvement in SOFA.

Based on those models, we will run simulations to explore scenarios for a larger trial.

5.4) SOFA

We intent to evaluate SOFA during ICU stay using hierarchical Bayesian linear regression models assuming intercept and slope hierarchical effects to patient to include individual time dependence, adjusted for baseline SOFA, and interaction of time and allocated device (coated or habitual). All priors shall be non-informative Normal distributed.

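### The Poisson intercept prior is printed as N(e^0.08, 5), which is not centred on 8 per 100 patient-days, and the per-group precision figure in SAP 3.4 has lost a 100

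*SAP*

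**What the plan says.** Section 5.2 says that sepsis incidence "will be estimated via Bayesian *Poisson* regression model with intercept parameter" and describes a "normal prior centered in 8 event per 100 patient-day incidence rate, $N(e^{0.08}, 5"). Section 3.4 has the same prior, a "normal prior centered in 8 event per 100 patient-days incidence rate, $N(e^{0.08}, 5"). Section 5.3 prints it a third time for a model that "will be done to estimate other infection incidences (VAP, CRBSI, CAUTI"), and uses the same model to compare coated with habitual devices: "Results will be reported as Risk Ratios (RR) with 95% Credible Intervals".

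Section 3.4 also holds the SAP's only statement of what 100 patients will deliver: "95% credible intervals with approximately 3 events per 100 patient-days overall (4 events per patient-day per group"). It adds of the prior: "The prior has a very large standard deviation, giving virtually no importance to its average choice". The centre of 8 is explained there as somewhat worse than a reference rate of 5 per 100 patient-days.

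**The concern.** The words and the formula for the primary model's prior stand side by side and describe different distributions. The exponential appears where a logarithm would be expected. An analyst who codes the words and one who codes the formula will fit different priors, and the SAP does not say which governs. The same formula carries over to the device-specific infections in section 5.3, where events may be few and a prior has more influence. Section 5.3 also bases its simulations for a larger trial on these models.

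The precision statement changes units in mid-sentence. As printed, the per-group figure equals 400 events per 100 patient-days, set beside an overall figure of 3 per 100.

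**Working it through.** **1. Prior centre**

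Inputs: stated centre 8 per 100 patient-days = 0.08 per patient-day; printed centre e^0.08 (sections 3.4, 5.2, 5.3). The SAP does not name the link. A log link is assumed, as is standard for Poisson regression and as the risk ratios in 5.3 imply, so rate = exp(intercept).

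e^0.08 = 1.083. The possible readings are:

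| Reading of e^0.08 | Exposure in patient-days | Exposure in units of 100 patient-days |
|---|---|---|
| Mean of the log rate: exp(1.083) = 2.954 | 295 per 100 | 2.95 per 100 |
| The rate itself (log mean 0.08): 1.083 | 108 per 100 | 1.08 per 100 |

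None gives 8. The first is 295.4 / 8 = 37 times too high and the second 108.3 / 8 = 13.5 times. The centre that matches the words is log(0.08) = -2.526 per patient-day, or log(8) = 2.079 if exposure is counted in hundreds.

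**2. Effect on the estimates**

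Posteriors were computed on a fine grid for the log rate, with a Poisson likelihood and a normal prior with SD 5. Exposure was in patient-days. The event counts and patient-days are assumptions, because the SAP gives no expected exposure. All results are per 100 patient-days.

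| Assumed data | Described centre, -2.526 | Printed centre, 1.083 |
|---|---|---|
| 80 events, 1,000 days: mean (95% interval) | 8.00 (6.34 to 9.85) | 8.01 (6.36 to 9.86) |
| 40 events, 800 days: mean | 5.00 | 5.02 |
| 40 events, 500 days (one group): mean | 8.00 | 8.03 |
| 0 events, 1,000 days: upper limit | 0.177 | 0.216 (+0.04 absolute) |
| 1 event, 1,000 days: upper limit | 0.402 | 0.430 (+7%) |
| 5 events, 1,000 days: upper limit | 1.039 | 1.059 (+2%) |
| 10 events, 1,000 days: upper limit | 1.718 | 1.737 (+1.1%) |

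**3. Precision per group**

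Inputs: overall figure 3 per 100 patient-days (section 3.4); 1:1 allocation (section 3.1), so each group has half the exposure T.

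- Approximate 95% interval length = 2 x 1.96 x sqrt(rate / T). Halving T multiplies the length by sqrt(2), whatever T is.
- 3 x sqrt(2) = 4.24 per 100 patient-days per group.
- Check with the Bayesian model and the described prior: a length of 3 per 100 needs T = (2 x 1.96)^2 x 0.08 / 0.03^2 = 1,366 patient-days at 8 per 100. The grid posterior length is 2.99 for 109 events in 1,366 days and 4.25 for 55 events in 683 days. At 5 per 100, T = 854; the lengths are 3.00 (43 events) and 4.19 (21 events in 427 days).

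So 4 fits as 4 per 100 patient-days. As printed, 4 per patient-day is 400 per 100.

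The overall 3 cannot be verified without an expected exposure. With an assumed 5 to 20 days per patient and rates of 5 to 8 per 100, the length runs from about 2.0 to 5.0, so 3 is plausible.

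**The case against.** The strongest reply is that this is notation and changes nothing. The SAP says the prior's centre hardly matters, and the sepsis rows of the table bear it out. Even the described prior, with SD 5, has a 95% range from about 0.0004 to 144,000 events per 100 patient-days. The intended centre is clear from the words, and the Stan code is not shown, so it may well be right. A rate of 4 sepsis events per patient per day is impossible, so nobody would act on it. The larger shifts arise only with very few events, in exploratory outcomes, and on assumed data.

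Most of this stands, and it is why the point is minor. It does not make the formula correct. Three identical printings make a text-extraction fault unlikely, and an evident misprint in the only precision statement still needs correcting.

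Two further cautions are fair. The sqrt(2) ratio applies to half-widths as well as to full lengths, so it confirms the unit but not which quantity is meant; the sentence in 3.4 is too garbled to settle that. And in the covariate-adjusted comparison of 5.3 the intercept is the log rate at reference covariate values, not the overall rate. The SAP's words give the same centre there, and with SD 5 the difference is negligible.

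**Conclusion.** Both errors are real and both are minor. The printed prior does not have the stated centre under any of the readings tried, and the per-group precision is 100 times too large as written. The sepsis estimate shifts by under 0.5% in the illustrated cases. For VAP, CRBSI or CAUTI, the upper limit moves by 1% to 7% with 10 down to 1 events in 1,000 patient-days, and by 0.04 per 100 with none. The sample size and the primary conclusion are unaffected.

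This rests on a log link, on reading the 5 as a standard deviation (which section 3.4's wording supports but does not say outright), and on assumed counts and exposure. If the 5 were coded as a variance, the shift would be larger: at an assumed 2 events in 500 days the posterior median would be 0.588 with the printed centre against 0.455 with the described one (+29%). That departs from the SAP's own wording and does not raise the weight of the point, but it is a reason to label the 5.

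**What to change.** - In 3.4, 5.2 and 5.3, write the prior as N(log(0.08), SD 5) on the log rate per patient-day, and state the log link and the log patient-days offset. If exposure is coded in units of 100 patient-days, the equivalent centre is log(8).
- Check that the Stan code uses that centre, that exposure unit and an SD of 5.
- In 3.4, change the per-group figure to about 4 events per 100 patient-days, and say that 3 and 4 are 95% credible interval lengths, if that is what is meant.

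The cost is wording in three sections and, if the code follows the printed formula, one line of Stan. No extra patients are needed and the design does not change.

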- To assess feasibility of the simultaneous insertion of coated and uncoated ETT, CVC and UC in recently admitted critically ill patients without previous invasive devices in a randomized controlled trial.
- To determine how many patients admitted to the ICU will require CVC, ET and UC insertion and, of those, how many will develop sepsis from 48 hours after randomization until day 28 after randomization or until ICU discharge.

Secondary objectives (clinical outcomes):

- Occurrence of nosocomial sepsis up to 28 days after randomization in control (uncoated devices) versus intervention (coated devices) groups
- Combined endpoint of any of the following infections occurring during ICU stay: Ventilator associated pneumonia (VAP), Catheter related bloodstream infection (CRBSI) and Catheter associated urinary tract infection (CAUTI).
- Occurrence of each nosocomial infection individually (VAP, CRBSI, CAUTI) in both groups and rates of positives cultures at each site.
- ICU and Hospital mortality in both groups.

3. Study methods

The full methods section, including detailed intervention and eligibility (inclusion and exclusion criteria), is explained in the Protocol.

3.1) Trial design

Pilot exploratory, randomized, open label, controlled trial. Critically ill patients which will demand placement of invasive devices for organ support (endotracheal tube, central venous catheter and urinary Foley catheter) will be randomized 1:1 to receive coated (Bactiguard®) or habitual (non-coated) devices.

3.2) Method of randomization and concealment allocation

Randomization list will be electronic generated using appropriate software and will be done in blocks stratified by site and by the presence of sepsis at randomization. Allocation group will only be informed after patient register in the electronic database, thereby preventing the investigator of anticipating for which group the patient will be randomized. Due to technical reasons, there will be no blinding.

3.3) Outcomes

The analysis of the two main outcomes involves both the feasibility of the study and the need to obtain epidemiological data on the occurrence of nosocomial sepsis after ICU admission. The feasibility will be assessed by study recruitment rate and by local input on the challenges of the randomization process. We expect a recruitment rate of approximately 1.3 patients a month per site.

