We may also test some nonlinear relation of SOFA on time in each group using polynomial or natural cubic splines. And evaluate alternatives to control death censoring (REF - <http://dx.doi.org/10.1136/bmj.j5748>) if mortality seems different between arms.

Results will be presented with proper graphs to highlight SOFA variation on time.

5.5) Subgroup analysis

Subgroup analysis will be tested by including interaction effect parameter into the model previously described in section 5.3. The only planned subgroup variable is the stratification characteristic: presence/absence of sepsis at admission.

5.6) Safety and Adverse Events

All reported Safety and Adverse events as described in the protocol will be presented with absolute and relative frequencies and tested with regular Fisher exact test between study groups (Coated vs. Habitual devices).

5.7) Missing data and imputation

We expect minimal missing data; none data imputation is planned.

6. Statistical software

Analyses will be done using R software (R Core Team, 2019). Bayesian models will be adjusted using *rstan* package (Stan Development Team, 2019).

REFERENCES

Nicolle LE. Catheter associated urinary tract infections. *Antimicrob Resist Infect Control*. 2014 Jul 25;3:23

Stan Development Team (2019). RStan: the R interface to Stan. R package version 2.19.2. <http://mc-stan.org/>.

R Core Team (2019). R: A language and environment for statistical computing. R Foundation for Statistical Computing, Vienna, Austria. URL <https://www.R-project.org/>.

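### Randomisation is stratified by site and sepsis, but the arm-comparison models in SAP 5.3 adjust for sepsis only; with site unmodelled, the credible interval may be modestly too narrow

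*SAP*

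**What the plan says.** - **SAP 3.1 and 3.2.** Patients "will be randomized 1:1 to receive coated (Bactiguard®) or habitual (non-coated) devices", and the randomisation "will be done in blocks stratified by site and by the presence of sepsis at randomization". That is two stratification factors.
- **SAP 5.3**, coated-versus-habitual Poisson models: "Models will be adjusted for admission type, baseline SOFA and the stratification variable (presence of sepsis at randomization". Stratification is in the singular and only sepsis is named.
- **SAP 5.5** does the same: "The only planned subgroup variable is the stratification characteristic: presence/absence of sepsis at admission".
- **SAP 5.4**, the SOFA model, is specified "assuming intercept and slope hierarchical effects to patient to include individual time dependence, adjusted for baseline SOFA, and interaction of time and allocated device". Neither stratification factor is listed.
- **SAP 5.2**, the primary incidence estimate, is an intercept-only model with no arm effect.

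Site therefore appears in the randomisation and in no analysis model. Section 5.3 ends by saying that its models will be the basis of simulations for a larger trial.

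**The concern.** The SAP adjusts for sepsis because it is a stratification factor, then leaves out the other factor without comment. The singular wording in 5.3 and 5.5 reads like an oversight rather than a decision.

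The SAP gives grounds to expect recorded event rates to differ by site. In 3.3 a new antibiotic class triggers the sepsis investigation, and CAUTI requires the attending physician to believe there is an infection and to prescribe. In 5.3, events as reported by the centres are analysed alongside adjudicated ones, with new antibiotic use part of the sepsis definition. Local prescribing habits therefore feed the outcome.

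Blocks within site balance numbers of patients, whereas the model works on patient-days. With 100 patients spread over site-by-sepsis strata, many blocks will also be incomplete. Some chance imbalance of exposure between high-rate and low-rate sites remains, and a model without site makes no allowance for it. At stake are the width of the exploratory rate-ratio interval and the variance structure handed to the larger-trial simulations.

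**Working it through.** **1. The plan's own precision figure.** For "This is a pilot study including 100 unique patients", section 3.4 gives "95% credible intervals with approximately 3 events per 100 patient-days overall (4 events per patient-day per group" as the interval length (the per-group figure presumably also per 100 patient-days). With a near-flat prior, length ≈ 2 × 1.96 × √(rate/T), where T is total patient-days. T is not stated, so solve for it at length 0.03:
- rate 0.08 (the prior centre): T = 0.08 × (3.92/0.03)² ≈ 1366, or 13.7 days per patient;
- rate 0.05 (the cited reference rate): T ≈ 854, or 8.5 days per patient.

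Halving T multiplies the length by √2: 3 × 1.414 = 4.24. The 3 and the 4 agree with each other. This figure is not in dispute; it shows only that exposure has to be assumed below.

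**2. Simulation A.** 1,500 runs per setting, 100 patients, no true effect, blocks of 4 within site by sepsis, mean 10 days at risk, 8 events per 100 patient-days, no exclusions. The log rate ratio was fitted with sepsis only, then with sepsis plus shrunken site effects. Number of sites, SD of log site rates, block size and exposure are assumptions.

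| Sites | Site SD | Bias, no site | Coverage, no site | Coverage, with site |
|---|---|---|---|---|
| 5 | 0.3 | 0.002 | 93.7% | 94.1% |
| 10 | 0.3 | 0.000 | 94.6% | 95.3% |
| 15 | 0.3 | 0.005 | 94.4% | 94.6% |
| 5 | 0.6 | 0.008 | 93.4% | 95.5% |
| 10 | 0.6 | 0.002 | 92.2% | 95.6% |
| 15 | 0.6 | −0.008 | 91.9% | 95.5% |

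Simulation error: for coverage √(0.95 × 0.05/1500) ≈ 0.6 percentage points; for bias about 0.26/√1500 ≈ 0.007. The biases are indistinguishable from zero. The coverage shortfall at SD 0.6 is real; at SD 0.3 it is small, at most about 1.3 points.

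The mechanism shows at 10 sites, SD 0.6. Without site the estimate varies with SD 0.252 while the model reports a standard error of 0.226. The ratio is 0.226/0.252 = 0.90, so the interval is about 10% too short, and 1.96 × 0.90 ≈ 1.76 corresponds to about 92% coverage, as observed. With site the figures are 0.229 and 0.233.

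**3. Simulation B.** 4,000 runs per setting, 10% lost after randomisation, median stay 8 days, about 5 events per 100 patient-days, a pooled rate ratio against a site-conditional one. Without site, coverage was 94–95% at SD 0.3–0.5 and 93% at SD 0.8 with 10–15 sites; with site it was 94.6–96%. At SD 0.8 the SD of the log rate ratio fell from about 0.345 to 0.333, or 0.012/0.345 ≈ 3.5%.

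**4. What these SDs mean.** The central 95% of sites spans exp(±1.96 × SD): 0.56 to 1.80 times the typical rate at SD 0.3, and 0.31 to 3.24 times at SD 0.6. An SD of 0.6 is a large difference between sites.

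**5. Exclusions after randomisation.** At SD 0.6 with 5 or 10 sites, random 15% exclusions left bias at −0.005 to −0.007 without site. A shift appeared only when coated-arm exclusions were made to cluster at high-rate sites (assumed 30% against 5%, habitual arm 10%): −0.077 and −0.069, that is rate ratios of about 0.93 when the truth is 1. With site, −0.029 and −0.024 remained.

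**6. Limits.** Neither simulation fitted the full planned model: admission type and baseline SOFA were left out. Simulation A set the shrinkage from the simulated site SD instead of estimating it, which favours the model with site. Neither simulation addressed SOFA.

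**The case against.** - **Bias.** A reader might infer that site differences enter the arm effect. The document does not support this: allocation is 1:1 in blocks within site, and the simulated bias is nil. This objection stands. What remains is chance imbalance that the interval does not reflect.
- **Exclusions.** A reader might infer bias through the post-randomisation exclusions in section 4. The shift to about 0.93 rests on exclusion rates that the SAP does not give. It would stem from section 4, and a site term reduces it without restoring the randomised comparison. It does not belong to this point.
- **SOFA.** A reader might infer that 5.4 leaves site variance in the error term. It does not: patients are nested in sites, so the patient-level intercepts absorb between-site differences in level. The contrast of interest is time by device, which a site intercept would change little.
- **Size and scope.** These are exploratory comparisons in a small pilot. With an SD of the log rate ratio near 0.34, the interval already runs a factor of about exp(1.96 × 0.34) ≈ 1.95 either way. Admission type and baseline SOFA may absorb some site case mix, and central adjudication may remove some differences in reporting. All this limits the importance of the point but does not explain the omission.
- **Few events per site.** An SD of 0.333 implies about 4/0.333² ≈ 36 events, or 2 to 4 per site with 10 to 15 sites. The site SD would lean on its prior. This stands, and the prior must therefore be stated. A reasoned choice to omit site would also be defensible, but none is given.

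**Conclusion.** The inconsistency is certain: two stratification factors in 3.2, one in 5.3 and 5.5, and site in no model. Its consequence is minor to modest. Omitting site does not by itself bias the arm rate ratio. It makes the 95% credible interval somewhat too narrow if sites differ substantially: 91.9–93.4% coverage at a site SD of 0.6, 93% at 0.8, and near nominal at 0.3–0.5. These figures are illustrative, because the SAP gives neither the number of sites nor the variation between them.

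The more practical loss is that the larger-trial simulations would be built on models with no between-site variance, a quantity needed to plan a multi-site trial. The primary incidence estimate in 5.2 is not affected by this point.

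**What to change.** - **5.3.** Put the stratification wording in the plural and name site as well as sepsis at randomisation. Add site as a random intercept to the arm-comparison Poisson models, with a stated weakly informative prior on its SD because events per site will be few. Otherwise, state why site is left out.
- **Simulations for the larger trial.** Carry the estimated site variance, with its uncertainty, into the scenarios.
- **5.5.** Say that sepsis is one of two stratification factors, and the only one planned as a subgroup.
- **5.4.** Adding the sepsis stratum and site is optional, for consistency; little change in the time-by-device contrast is expected.

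The cost is a wording change and one model term. Site is already known from randomisation, and the models are fitted in rstan. If sites do not differ, the interval is slightly wider: about 3–5% with fixed site effects, less with a random intercept.

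### Whether the SOFA comparison also accounts for death is decided after looking at mortality by arm, with no threshold, mortality endpoint or method fixed in advance

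*SAP*

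**What the plan says.** SAP section 5.4 states the main model: "We intent to evaluate SOFA during ICU stay using hierarchical Bayesian linear regression models", with patient-level intercepts and slopes, adjustment for baseline SOFA and a time-by-device interaction. It then allows for non-linear time trends. Its only provision for death is this: "And evaluate alternatives to control death censoring", with one methods paper cited, to be done "if mortality seems different between arms".

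No other section supplies a rule for death in this analysis. Section 5.7 says "We expect minimal missing data; none data imputation is planned" and does not mention deaths. Section 2.1 lists "ICU and Hospital mortality in both groups" among the clinical outcomes, so two mortality endpoints could serve as the trigger. Neither is given an expected rate.

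**The concern.** A patient who dies has no later SOFA score, and a patient discharged alive has none recorded in the ICU. The sickest and the fittest therefore both leave the data, for opposite reasons. A model fitted to what remains compares patients selected by events after randomization.

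The SAP recognises the problem but ties its response to a comparison of mortality by arm, judged by eye. Two things follow.

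- Whether readers see a SOFA result that accounts for death, and which method produces it, depends partly on chance and partly on the analyst's judgement once results are known.
- If mortality looks similar, nothing further is planned. Yet the two arms can lose different kinds of patients at the same overall rate, and the survivors then differ even when the device does nothing to SOFA.

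What is at stake is how the device comparison on SOFA is read: as a statement about all analysed patients, or only about those still alive in the ICU.

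**Working it through.** The SAP contains no figure on mortality to reproduce. The precision statement in section 3.4 concerns sepsis incidence and plays no part here.

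**Inputs from the SAP.** Section 3.4: "This is a pilot study including 100 unique patients". Section 3.1: patients "will be randomized 1:1 to receive coated" or habitual devices. Hence about 100 / 2 = 50 per arm. This is derived, not stated. Section 4 says of randomized patients who did not receive all three devices "Those cases were excluded from the analyses", so the arms are smaller if the 100 are counted before exclusion.

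**Inputs assumed, because the SAP gives none.** Mortality p of 20% to 50%; a trigger of 10 points, with 20 points as an alternative.

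**Step 1: precision of the mortality difference.** SE = sqrt(2p(1 − p)/50). At p = 0.40 this is sqrt(2 × 0.4 × 0.6/50) = 0.098. The 95% half-width is 1.96 × SE.

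**Step 2: how often each trigger fires or misses.** Let X and Y be the deaths in the two arms, independent binomials with n = 50. A gap of 10 points means |X − Y| ≥ 5, and one of 20 points means |X − Y| ≥ 10. Exact sums give:

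| Control mortality | 95% half-width (points) | Equal mortality: gap ≥ 10 | Equal mortality: gap ≥ 20 | True 10-point reduction: gap < 10 |
|---|---|---|---|---|
| 20% | 15.7 | 26% | 2% | 44% |
| 30% | 18.0 | 33% | 4% | 44% |
| 40% | 19.2 | 36% | 5% | 43% |
| 50% | 19.6 | 37% | 6% | 43% |

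A loose trigger fires by chance in a quarter to a third or more of trials, and still misses a true 10-point difference in over two fifths. A strict trigger seldom fires by chance, but a true 10-point difference would usually fall short of it: the observed gap is below 20 points in 82% to 90% of trials by the same sums. No cut-off performs well on both counts with arms of this size.

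**Step 3: does similar mortality protect the comparison?** An illustration with assumed inputs: SOFA has mean 8 and SD 3 in both arms, the device has no effect on SOFA, and 30% die in each arm. The log-odds of death per SOFA point are 0.3 in one arm.

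- 0.1 in the other arm: survivor means 7.29 and 7.73, a difference of 0.44 points.
- 0.2 in the other arm: 7.29 and 7.49, a difference of 0.20.
- 0.3 in both arms: no difference.

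Equal mortality is therefore not sufficient. What matters is who dies, which the trigger does not examine.

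**The case against.** **The clause adds analyses and replaces nothing.** This stands. Section 5.4 fixes the hierarchical model, and nothing says it is dropped. A reader might infer that the SOFA method as a whole is picked after the data are seen, but the text does not support that. What depends on the data is whether a death-inclusive analysis is added, and which one.

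**SOFA carries little weight.** This also stands. SOFA trajectory is neither a primary nor a secondary objective, the sample size does not rest on it, the trial is an exploratory pilot, and section 5.4 is worded tentatively. This limits the severity. It does not justify leaving the choice open, since fixing such choices is the purpose of a SAP.

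**The trial is open label, so outcomes by arm are visible anyway.** True, and for that reason the objection here is to the missing rule and not to loss of blinding.

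**The figures rest on an invented mortality and cut-off.** Both are assumptions, and the chance-firing rate depends heavily on the cut-off, as the table shows. A reader might take the 26% to 37% as a property of the plan. It is not: the SAP states no cut-off, which is itself part of the defect.

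**A mixed model already copes with dropout.** Only in part. Under missing-at-random it treats scores after death as values that exist but were not observed, so truncation by death is not addressed.

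**No bias in the planned model has been shown.** Correct. Step 3 compares raw survivor means under assumed death mechanisms that differ by arm. It does not fit the planned model with baseline SOFA. It shows that equal mortality gives no guarantee, not how large the bias would be in this trial.

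**Conclusion.** The point holds in a limited form. Section 5.4 makes any death-inclusive SOFA analysis conditional on an undefined impression of mortality by arm, and no other section gives a default. The condition is set after the fact and asks the wrong question. With about 50 per arm and mortality anywhere from 20% to 50%, the mortality difference is known only to within about 16 to 20 points either way. The trigger is therefore an unreliable guide whichever cut-off is used.

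This conclusion rests on the derived arm size and the assumed mortality range. It does not depend on a particular cut-off. The documents do not support the stronger claim that the reported SOFA effect will be biased by a known amount. Since SOFA is an exploratory analysis in a pilot, the point is minor to moderate.

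**What to change.** In section 5.4, delete the condition on mortality. Name one death-inclusive sensitivity analysis in advance and report it whatever mortality is observed. Examples are a longitudinal ordinal model with death as the worst state, or a joint model of SOFA and death. They answer different questions, so the estimand should be stated with the choice. The analysis should cover the period in which SOFA is recorded, with a written rule for patients discharged alive.

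Keep the planned hierarchical linear model, labelled as describing SOFA while alive in the ICU. Any further method can be listed as exploratory.

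The cost is one extra model and a short paragraph in the SAP, including the discharge rule. The SAP lists ICU and hospital mortality as outcomes but does not say that the timing of death is recorded. The sponsor should confirm this before choosing a method that needs it.
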